Studies have compared the accuracy of the landmark-based joint line approach to that of other injection approaches in the knee. One study compared the accuracy of anteromedial, anterolateral, and lateral midpatellar over a series of 240 injections.⁶ All of these injections were landmark based (no ultrasound used for the procedure) and patients with an effusion were excluded from participation. The lateral midpatellar approach was found to be the most accurate (93%) compared to the anteromedial (75%) and anterolateral (72%) approaches.⁴ Taken one step further, Esenyel et al compared the accuracy of four different approaches to knee injection in 78 cadaveric knees: anteromedial joint line, anterolateral joint line, lateral midpatellar, and medial midpatellar.⁷ This particular study found the anterolateral approach to be the most accurate at 85% success versus 73% for anteromedial, 76% for lateral midpatellar, and 56% for medial midpatellar. Overall these studies show that the anterolateral aspect of the suprapatellar pouch may result in the highest accuracy for landmark-based injections.

Although ultrasound-guided injections are superior to surface landmark-guided techniques into the subacromial space (defined as the extra-articular area between the superior aspect of the humerus and the inferior surface of the acromion) of the shoulder; there are no consistent data regarding landmark-guided versus ultrasound guided

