techniques for accuracy of injections specific to the knee joint. One study compared landmark-based and ultrasound-guided techniques in 184 patients receiving corticosteroid injections of their shoulder, elbow, wrist, knee, or ankle³. In aggregate, ultrasound-guided injections were found to be more accurate (83%) compared to clinical examination-guided injections (66%). However, this study was not powered to determine a difference in accuracy among the individual joints. Self-reported pain and function scores at two and six weeks following the injection were no different based on the technique employed. There was, however, a trend towards improvement in function based on a visual analog scale at two weeks post ultrasound-guided injection and a statistically significant improvement at six weeks post injection. Additionally, a trend was seen for improvement in pain (VAS scale) at two and six weeks post injection. Although there was lack of power to adequately reach a conclusion, this study suggests a potential therapeutic benefit with ultrasound-guided injections of the knee versus a landmark-based technique.

Wiler et al, compared the amount of fluid aspirated from 66 knee joints by emergency department physicians using an ultrasound-guided suprapatellar versus a landmark-based joint line approach.⁴ This study found no difference in amount of fluid aspirated. However, participants reported significantly less pain when the ultrasound guided approach was used (3.71 versus 5.19 on a 10-cm VAS scale). Providers believed that the ultrasound approach was easier to perform (1.67 versus 2.11 units on a five-point scale) and the procedure time was shorter (10.58 versus 13.37 minutes). No analysis of target acquisition accuracy was obtained in this study.

One study showed increased accuracy of injections into the knee with ultrasound guidance, but the researchers used a medial midpatellar approach.⁵ With this technique the patient lies supine and the needle is inserted medially at the patellofemoral joint line at the midpoint between the superior and inferior patellar poles . Among 89 injections, ultrasound guided medial midpatellar injections were found to have an accuracy rate of 95.6% compared to 77.3% with a landmark-guided medial midpatellar injection. However, the theoretical disadvantage to this technique in damage to the cartilage from the needle tip, a risk that typically precludes this approach from our standard practice.

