- **a.** There will be a Research Coordinator at the trial site who will administer the consent and HIPAA authorizations. This will be performed with a standardized consent form (Appendix A), including a scripted discussion of the study procedures and a scripted discussion of risks inherent in the injection techniques
- **b.** Upon completion of consent, the Coordinator will have the subject explain their understanding of the concept of treatment in their own words to ensure the subjects understand the consent.

Study Design

The study will be a randomized, double-blinded clinical study comparing four techniques for intra-articular knee injections.

The study investigators will receive a list of 120 computer generated random numbers from

Page 8 of 17 Version 2.0 one to four. No more than 30 will be in each group to ensure that each group is the correct size. Upon entry into the study, and prior to the first injection, subjects will randomized by selecting a sealed envelope from a box containing an equal number of envelopes for each of the four treatments groups. The envelope will be given, unopened, to the study doctor. The subject will be blinded to their study group assignment.

Double-blinding will be done as follows: The subjects will be blinded to whether ultrasound was used to guide their treatment. The radiologist, who will review the fluoroscopic images after the injections, will be blinded to treatment group assignment. The injecting physician will not be blinded to the treatment group assignment. Treating physicians (injecting physicians) will perform the technique as detailed below based on the assignment of the participant. Subjects and the radiologists will both be asked to guess their treatment group at each point in the data collection to determine the effectiveness of the blinding process. The Surveyor will also be blinded to the treatment group allocation.

The injecting physicians will consist of orthopedic surgeons, sports medicine fellows, or sports medicine fellowship trained primary care physicians. All injecting physicians will receive a minimum of 2 hours of hands-on training specific to the procedures employed in this study. Additionally, they will be supervised for their first several ultrasound-guided procedures to assure competence with the techniques.

Study Methodology/Procedures

Appointment 1

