Safety Monitoring and Analysis Plan

Since treatments are provided at the onset of the study, "stopping rules" will not apply in this study. Since the primary outcome includes pain and functioning at baseline and 3 months following the intervention, the entire study must be carried out in order to gather the desired data. There have been no unexpected side effects other than local pain and swelling at the injection site that have been reported in the studies using these injection techniques, so we do not believe any other specific side effects will need to be monitored. Patients will not be included in the study if a contraindication applies to them. Of note, viscosupplementation is not contraindicated in pregnant patients.

Sample Size Estimation

For the comparison of accuracy, a two group chi square test with a 5% two-sided significance level will have 80% power to detect a difference of 33 percentage points between groups when the accuracy in the less-accurate condition is 60% and the sample size in each group is 25.

Previous studies have demonstrated an effect size of the WOMAC ranging from 0.5 to 1.0 when medication interventions were studies on patients with knee pain. A sample size of 25 in each group will have 80% power to detect an effect size of 0.809 using a two group t-test with a 5% two-sided significance level.

Reference: Lenth, R. V. (2006-9). Java Applets for Power and Sample Size [Computer software]. Retrieved November, 2010, from http://www.stat.uiowa.edu/~rlenth/Power.

Reporting Adverse Events

Definitions:

Adverse events (adverse effects, adverse reactions): any occurrence of injury, dysfunction, disease, or abnormality of any organ or tissue that occurs in a subject enrolled in a clinical protocol. Manifestations of an adverse event may include symptoms, physical exam abnormalities, diagnostic study abnormalities, and/or death.

Expected adverse events: adverse events previously known or anticipated to result from: 1) the interventions and interactions used in the research (these events must be included as potential risks in the consent form); 2) the collection of identifiable private information under research (these events must be included as potential risks in the consent form); 3) an underlying disease, disorder, or condition of the human subjects; and/or 4) other circumstances unrelated to the research or any underlying disease, disorder, or condition of the subject.

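### The 60% base rate and 33-point difference behind the 80% accuracy power are unsourced and out of line with the protocol's cited landmark joint-line rates of 72–85%; arm-against-arm power for the cited 18–21-point knee differences is about 41–58%

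*Combined protocol and SAP*

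**What the plan says.** Sample Size Estimation bases the accuracy comparison on "a two group chi square test with a 5% two-sided significance level", and claims that this test "will have 80% power to detect a difference of 33 percentage points between groups". The claim is tied to one base rate and one group size: it applies "when the accuracy in the less-accurate condition is 60% and the sample size in each group is 25". The better condition is therefore at 93%. The less accurate condition is not named, and neither the 60% nor the 33 points has a source.

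The Literature Review gives these landmark joint-line rates:

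- In a series of 240 injections in patients, the lateral midpatellar approach was "found to be the most accurate (93%) compared to the anteromedial (75%) and anterolateral (72%) approaches".
- A cadaver study "found the anterolateral approach to be the most accurate at 85% success versus 73% for anteromedial".

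The one knee-specific accuracy comparison of ultrasound with landmark used a medial midpatellar approach. Its ultrasound-guided injections "were found to have an accuracy rate of 95.6% compared to 77.3% with a landmark-guided medial midpatellar injection". A study of five joints together gives 83% v 66%. No accuracy rate is cited for landmark suprapatellar injection.

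Study Design plans 120 participants and says "No more than 30 will be in each group to ensure that each group is the correct size". Data Analysis compares percent accuracy among the four groups by chi-square tests and does not mention combining groups.

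**The concern.** Presence of contrast in the joint is a named primary endpoint, and Aims 1 and 2 are both about accuracy. If the planning inputs do not fit the arms being compared, the stated 80% tells the reader little about what the trial can detect. The contrast most exposed is ultrasound against landmark at the joint line (Group 1 v Group 2), which is part of Aim 2. On the cited rates its landmark arm starts at 72% or higher, so there is no room for a 33-point gain. A non-significant pairwise result could then be taken as evidence that guidance does not help, in a trial believed to have 80% power, when its chance of finding a plausible benefit was nearer one half.

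**Working it through.** **Inputs.** Two-sided 5% and 25 per group (Sample Size Estimation); 30 per group (Study Design); accuracy rates from the Literature Review.

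**Formula.** Normal approximation to the uncorrected chi-square test, with n per group, Δ = p2 − p1 and p̄ = (p1 + p2)/2:

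power = Φ{ [Δ − 1.96 √(2p̄(1 − p̄)/n)] / √([p1(1 − p1) + p2(1 − p2)]/n) }

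Exact power sums the binomial probabilities of all pairs of counts for which the uncorrected chi-square statistic reaches 3.841.

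**Step 1: the plan's own figure.** With p1 = 0.60, p2 = 0.93 and n = 25, p̄ = 0.765. The null standard error is √(2 × 0.765 × 0.235/25) = 0.1199, and the alternative one is √((0.2400 + 0.0651)/25) = 0.1105. Then (0.33 − 1.96 × 0.1199)/0.1105 = 0.86, and Φ(0.86) = 0.805. Exact power is 0.845. The stated 80% reproduces, and the approximate formula matches it more closely.

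**Step 2: is 33 points possible?** It needs a base of at most 100 − 33 = 67%. The cited landmark joint-line rates give 72 + 33 = 105, 73 + 33 = 106, 75 + 33 = 108 and 85 + 33 = 118. None is attainable.

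**Step 3: power for the cited differences in patients' knees.** Worked example, 75% v 93% at n = 25: p̄ = 0.84, standard errors 0.1037 and 0.1005, (0.18 − 1.96 × 0.1037)/0.1005 = −0.23, power 0.409. All entries are approximate/exact:

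| Pair | Points | 25 per arm | 30 per arm | 50 v 50 | 60 v 60 |
|---|---|---|---|---|---|
| 75% v 93% | 18 | 0.409/0.440 | 0.476/0.500 | 0.695/0.733 | 0.774/0.788 |
| 72% v 93% | 21 | 0.498/0.537 | 0.575/0.601 | 0.798/0.832 | 0.867/0.881 |
| 77.3% v 95.6% | 18.3 | 0.471/0.515 | 0.546/0.597 | 0.770/0.817 | 0.843/0.871 |

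For 80% power by the approximate formula these pairs need 64, 51 and 54 per arm. The last two columns are for two arms combined on each side, taking the same pair of rates in both strata.

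**Step 4: difference detectable with 80% power (approximate formula).**

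| Base | 25 per arm | 30 per arm | 50 v 50 | 60 v 60 |
|---|---|---|---|---|
| 72% | 27.2 points | 25.5 | 21.1 | 19.6 |
| 75% | not reached (0.779 at 100%) | 23.9 | 19.9 | 18.5 |

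The exact calculation is somewhat kinder: at 25 per arm it gives 25.5 points from 72% and 23.6 from 75%. The method therefore has to be named beside any figure.

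**The case against.** Several points on the other side have weight.

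- **The 60% is conditional and attached to no arm.** A reader might infer that it contradicts the cited 72–85%. The documents do not go that far: it could describe the landmark suprapatellar arm, for which no rate is cited and whose pouch the protocol says can be hard to find without an effusion. It also lies between two cited landmark rates, 56% and 66%. This stands, so unsourced and out of line with the joint-line rates is the right description. But the Literature Review also suggests that the suprapatellar pouch may be the most accurate landmark site, which makes joint line the more natural less-accurate condition. Even on the suprapatellar reading, the stated power would not carry over to Group 1 v Group 2.
- **The comparison rates are not from the trial's techniques.** The 93% is landmark lateral midpatellar, and the 77.3% and 95.6% are medial midpatellar, an approach the protocol says it typically avoids. This stands, and the power figures are a guide only.
- **The choice of pairs matters.** At 25 and 30 per arm, approximate power is 28% and 32% for 66% v 83%, 18% and 20% for 73% v 85%, and 62% and 70% for 56% v 85%. Combining a 72% base with 95.6% gives 63% and 71%. The 41–58% belongs only to the three pairs tabulated.
- **Aims 1 and 2 read as two-condition contrasts.** Pooled, they would have about 70–87% power for those three pairs. This is true, but neither Data Analysis nor the calculation at 25 per group describes pooling.

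**Conclusion.** The point holds as a planning assumption that needs support or replacement. It is not an arithmetic error, because the 80% is correct for 60% v 93%. From the cited joint-line rates the planned difference cannot occur. For the three cited 18–21-point differences, single-pair power is about 41–50% at 25 per arm and 48–58% at 30 (exact 44–54% and 50–60%).

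A reader might go further and infer that a null pairwise result is the likely outcome even if guidance works as in the cited knee study. The figures do not support that: exact power for 77.3% v 95.6% is 0.52 at 25 per arm and 0.60 at 30, so a null is about as likely as not. Nor can it be said that adequate power is out of reach for the aims, since pooled contrasts come close to 80% or exceed it for most of these cases.

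These results assume an uncorrected chi-square test at two-sided 5% with no multiplicity adjustment. A continuity-corrected or Fisher test would have less power: for the plan's own 60% v 93% at 25 per arm, 69% and 73%.

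**What to change.** 1. **Sample Size Estimation.** Restate the accuracy power from the cited joint-line base rates, name the method, and give both 25 and 30 per arm. By the approximate formula, 25 per arm needs about 27 points from a 72% base and does not reach 80% from 75%; 30 per arm needs about 24–26 points. If 60% is kept for some arm, name the arm and give the source.
2. **Data Analysis.** Make the main accuracy test for Aim 2 ultrasound v landmark pooled over approach, for example stratified by approach, and for Aim 1 joint line v suprapatellar pooled over guidance. Base the stated power on these contrasts: from a 72–75% base, about 20–21 points at 50 v 50 or 19–20 points at 60 v 60.
3. **Single pairs.** Report differences between individual arms as estimates with confidence intervals.

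The cost is a reworded sample-size paragraph, an added analysis line and a less favourable stated power for single pairs, with no extra patients. The pooled test for Aim 2 assumes that guidance has a broadly similar effect in both approaches; if it does not, the pooled result is an average and the separate estimates must be read beside it.

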• Initial evaluation: Screening instrument for first visit (history and physical, diagnostic and inclusion/exclusion criteria), WOMAC (prior to receiving each of the three injections), and intervention

The clinical staff will collect the following data:

- Name, email, phone number
- Demographics: age, gender, type and number of injections received previously
- Informed consent/HIPAA document
- WOMAC Osteoarthritis Index
- Post Procedure

The Injecting physician will record the following data:

- Group Assignment
- Amount and type of therapeutic substance injected
- Total time to complete procedure from sterilization to bandaging
- Procedural Pain Score (0 to 10)
- Procedural Satisfaction Score (0 to 10)
- Complications

In a separate electronic database, the radiologist will record the following data:

- Name
- Presence or absence of contrast material within the knee joint
- Three months after intervention (telephone)
 - WOMAC Osteoarthritis Index
 - Procedure Satisfaction Score (0 to 10)

Study Time Line

Assessment					
Study Day /	Initial Evaluation	and	Second	Third Injection	3 months
Period	First Injection		Injection	With contrast	Post Treatment
Screening	Х				
Informed	Х				
Consent, discuss					
Plan, etc.					
Randomization	Х				
Demographics,	Х				
History &					
Physical					
WOMAC (pre	х		Х	Х	Х
injection)					
Treatment	X		Х	Х	
Procedural Pain	Х		Х	Х	
(post injection)					
Procedural	Х		Х	X	Х

Satisfaction (post injection)			
Fluoroscopic Analysis		Х	
Complications (post injection)		X	

Statistical Consideration

Primary endpoints are presence/absence of contrast medium in the joint, the WOMAC osteoarthritis index, and overall satisfaction with the injection technique. Our statistical analysis of the WOMAC index will consider a mean change from baseline to post-injection with the variables of pain, stiffness, and function. We will also study the mean change of the Global Score from the WOMAC.

Data Analysis

Statistical analysis of the WOMAC score will consist of one-way analysis of variance (ANOVA) followed by Tukey's post-hoc multiple comparisons between the four groups with a 5%, two-sided familywise significance level (which allows for comparisons between all possible pairs of treatments). Chi square tests will be used to compare the percent accuracy among the four groups. We will also perform sub-analysis to determine if any trends can be linked to the type of medication (viscosupplementation) injected versus accuracy.

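### The WOMAC sample size leans on effect sizes from medication studies, although every group receives hyaluronan and only the injection technique is randomized

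*Combined protocol and SAP*

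**What the plan says.** The protocol's Sample Size Estimation section has one paragraph on WOMAC. It states that "Previous studies have demonstrated an effect size of the WOMAC ranging from 0.5 to 1.0 when medication interventions were studies" in people with painful knees. It then claims "80% power to detect an effect size of 0.809 using a two group t-test" for 25 patients per group, tested two-sided at 5%. No other basis for a WOMAC effect is given. The paragraph does not say whether 0.5 to 1.0 is a between-group or a before-after effect, or which SD it uses.

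For accuracy, the same section claims "80% power to detect a difference of 33 percentage points between groups" when the less accurate condition reaches 60%.

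The Data Analysis section plans a different WOMAC test from the one that was powered: a one-way ANOVA, then Tukey's "post-hoc multiple comparisons between the four groups with a 5%, two-sided familywise significance level". The Study Design section caps each group at 30, for 120 in total.

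The group descriptions under Study Methodology/Procedures give hyaluronic acid to all four groups. The product may vary between patients, but it is not set by group. Statistical Consideration names WOMAC as a primary endpoint, and Scientific Justification makes pain and functioning by technique one of three primary questions.

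**The concern.** An effect size supports a sample size only if it belongs to the contrast being tested. A range from medication studies describes what a drug does. This trial asks whether the route to the joint, or ultrasound guidance, changes the result of a treatment that everyone receives. Nothing in the protocol says how large that difference is expected to be.

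A reader of the section sees 0.809 inside a cited range of 0.5 to 1.0, next to a claim of 80% power, and may take WOMAC to be adequately powered for technique. If the true technique effect is at or below the low end of the range, a non-significant result would be likely and would say little. It could still be taken to mean that technique makes no difference to patients.

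**Working it through.** **Inputs.** From Sample Size Estimation: d = 0.809, 25 per group, two-sided 5%, two-group t-test; cited range 0.5 to 1.0; detectable accuracy difference 33 points from 60%. From Study Design: at most 30 per group. From Data Analysis: Tukey on all 6 pairs of four groups, familywise 5%.

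**Step 1: the plan's own figure.** The noncentrality is d × √(n/2) = 0.809 × √12.5 = 2.860, with 48 degrees of freedom and critical value 2.011. Noncentral-t power is 80.0%, and the effect detectable with 80% power is 0.809. The stated figure reproduces.

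**Step 2: the cited range and the planned test.** For Tukey, the critical value for one pair is the 95% studentized-range point for four groups divided by √2. This is 2.615 with 96 degrees of freedom (25 per group) and 2.607 with 116 (30 per group). Power for one pair:

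| Effect (SD) | t-test, n = 25 | t-test, n = 30 | Tukey, n = 25 | Tukey, n = 30 |
|---|---|---|---|---|
| 0.5 | 41.0% | 47.8% | 20.5% | 25.6% |
| 0.809 | 80.0% | 86.9% | 59.8% | 70.0% |
| 1.0 | 93.4% | 96.8% | 81.9% | 89.5% |

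Under Tukey, 80% power for one pair needs 0.98 SD with 25 per group, or 0.89 SD with 30. If a significant ANOVA is required before the pairwise step, power cannot be higher than shown.

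**Step 3: what a null result would exclude.** The 95% half-width for one unadjusted pair with 25 per group is 2.011 × √(2/25) = 0.57 SD. An observed difference of zero would not exclude 0.5 SD.

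**Step 4: an illustration of a technique effect.** Assume that technique acts only through accuracy, that the accuracy difference is 33 points, that a missed injection gives no benefit and a hit gives all of it, and that 0.5 to 1.0 is a between-group effect on the same SD scale. Then the WOMAC difference is 0.33 × 0.5 = 0.165 to 0.33 × 1.0 = 0.33 SD. Unadjusted power is 8.8% to 20.8% with 25 per group, and 9.6% to 24.2% with 30.

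The result moves with the assumptions (25 per group, unadjusted):

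- With the ultrasound v landmark accuracy gaps cited in the Literature Review (83 − 66 = 17 points; 95.6 − 77.3 = 18.3 points), the effect is 0.085 to 0.183 SD and power 6% to 10%.
- If the cited 0.5 to 1.0 was itself obtained with only 60% to 75% of injections in the joint (an assumption), the effect is 0.33 × 0.5/0.75 = 0.22 to 0.33 × 1.0/0.60 = 0.55 SD and power 12% to 48%.
- Over three independent injections at 60% v 93%, if one hit is enough, the gap is (1 − 0.07³) − (1 − 0.40³) = 6.4 points, giving 0.03 to 0.06 SD and power 5% to 6%.
- If all three must hit, the gap is 0.93³ − 0.60³ = 58.8 points, giving 0.29 to 0.59 SD and power 17% to 53%.

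**Step 5: the pooled ultrasound contrast.** With 30 per group, pooling over approach gives 60 v 60. The unadjusted effect detectable with 80% power is 0.52 SD, power at 0.5 SD is 78%, and the 95% half-width is 1.980 × √(2/60) = 0.36 SD. With 25 per group (50 v 50), the detectable effect is 0.57 SD and power at 0.5 SD is 70%.

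**The case against.** The strongest defence is that the sample-size sentence is a correct conditional statement: 25 per group gives 80% power if the effect is 0.809 SD. The protocol never says that it expects 0.809 between techniques. That stands as far as it goes. It does not rescue the medication range, which is the only support offered and belongs to another contrast. It also does not cover the mismatch with the Tukey test.

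A reader might infer something stronger: that the plan's own figures imply a technique effect of 0.17 to 0.33 SD and 9% to 21% power. The documents do not support that.

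- The 33 points is what the accuracy test can detect, not what is expected.
- The protocol does not say what a missed injection is worth, how hits accumulate over three injections, or whether 0.5 to 1.0 is a between-group effect.
- It describes routes other than accuracy. The suprapatellar ultrasound procedure includes aspiration of an effusion or saline dissection. The joint-line ultrasound procedure includes a saline bolus, and the joint-line landmark procedure describes neither step. The background names avoiding contact with cartilage as a possible advantage of the suprapatellar approach.

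A reader might also cite the Literature Review as evidence that technique does not affect symptoms, since in one mixed-joint corticosteroid study "Self-reported pain and function scores at two and six weeks following the injection were no different based on the technique employed". The same paragraph reports a significant gain in function on a visual analog scale at six weeks with ultrasound, trends in pain, and a lack of power. The cited evidence is mixed. It supports neither a null effect nor one of 0.8 SD.

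**Conclusion.** The concern holds in a limited form. The medication range does not justify the WOMAC comparison, and no technique effect is stated. The 80% applies to one unadjusted pair at 0.809 SD with 25 per group. For the planned Tukey comparison it is about 60% with 25 per group and 70% with 30. At 0.5 SD power is 41% or 48% unadjusted, and about 20% or 26% under Tukey. Only near the top of the cited range, at 1.0 SD, does the Tukey test pass 80%.

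These figures assume equal groups, a common SD and no loss to follow-up; the protocol states no dropout rate. The 0.17 to 0.33 SD and 9% to 21% are an illustration under assumptions that the documents do not make. Other readings in the working give 5% to 53% with 25 per group, and all of them stay below 80%. The protocol also nowhere says that non-significance will be read as equal benefit; the point is that it does not rule this out.

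**What to change.** In Sample Size Estimation:

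- Remove the medication effect-size range as justification. If the sponsor has an expected WOMAC difference between techniques, state it with its source.
- State that 25 per group gives 80% power at 0.809 SD for one unadjusted pair, and give the power of the planned Tukey test beside it (about 60% with 25 per group, 70% with 30).

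In Data Analysis:

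- Add the ultrasound v landmark WOMAC contrast pooled over approach, with a 95% interval, labelled as one contrast outside the Tukey family. With 60 v 60 it has 80% power at about 0.52 SD unadjusted, assuming no large approach-by-ultrasound interaction.
- State that a non-significant WOMAC result will not be read as equal benefit, and that the interval will carry the interpretation.

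The cost is wording, one extra contrast and a more modest WOMAC power claim; no extra patients are needed. Moving WOMAC to secondary is an option for the sponsor but not required, since patient-perceived pain and function is a stated aim. A power figure of 10% to 20% should not be written into the protocol as fact, because it rests on the illustrative assumptions.

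### The stated 80% WOMAC power is for one unadjusted two-group t-test; under the planned Tukey comparisons a given pair has about 60% (25 per group) to 70% (30 per group).

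*Combined protocol and SAP*

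**What the plan says.** Statistical Consideration names the WOMAC index as one of the primary endpoints. Data Analysis assigns it "one-way analysis of variance (ANOVA) followed by Tukey's post-hoc multiple comparisons between the four groups", at a "5%, two-sided familywise significance level (which allows for comparisons between all possible pairs of treatments"). Four groups give six pairs.

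Sample Size Estimation says that 25 per group "will have 80% power to detect an effect size of 0.809 using a two group t-test with a 5% two-sided significance level". It also cites WOMAC effect sizes between 0.5 and 1.0 from earlier medication studies.

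Study Design provides for 120 patients, equally divided: "No more than 30 will be in each group to ensure that each group is the correct size". The documents do not explain the step from 30 to 25. They give no expected dropout rate, no power for the ANOVA or the Tukey comparisons, and no allowance for multiplicity in the sample size.

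**The concern.** The power statement and the analysis plan describe different tests of the same primary endpoint. One is a single two-group t-test with the whole 5% to itself. The other shares 5% across six comparisons, so each pair must clear a higher bar. At a fixed sample size, that costs power.

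The third aim is to examine differences in pain and function after the injection series, and Scientific Justification asks whether these depend on the technique. Specific pairs therefore matter. A reader could take each planned pairwise WOMAC comparison to have 80% power at 0.809, and so read a non-significant pair as firmer evidence of no difference than it is.

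**Working it through.** **Inputs.** From Sample Size Estimation: 25 per group, effect size d = 0.809 in SD units, two-sided 5%, 80% power. From Data Analysis: four groups, Tukey for all pairs, 5% familywise. From Study Design: at most 30 per group. Assumed throughout: normal outcomes, a common SD and equal group sizes.

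**Step 1: the plan's own figure.** For a two-group t-test, df = 2(n − 1) and the noncentrality is d × √(n/2).

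- n = 25: df = 48, critical value 2.011, noncentrality 0.809 × √12.5 = 2.860.
- Power from the noncentral t is 0.800, so the stated figure reproduces.

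**Step 2: the planned test, one given pair.** Tukey declares a pair different when |t| exceeds q(0.95; 4, df)/√2, with the pooled error df = 4(n − 1). The noncentrality formula is unchanged.

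| | n = 25 | n = 30 |
|---|---|---|
| df | 96 | 116 |
| q(0.95; 4, df) | 3.698 | 3.686 |
| Critical value q/√2 | 2.615 | 2.607 |
| Equivalent per-pair level | 0.0104 | 0.0103 |
| Noncentrality at 0.809 | 2.860 | 3.133 |
| **Power, given pair** | **0.598** | **0.700** |
| Effect size with 80% power | 0.980 | 0.892 |

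The miss rate for a given pair at 0.809 is therefore 1 − 0.598 = 40% or 1 − 0.700 = 30%, against the 20% implied. Over the cited range of effect sizes, 0.5 to 1.0, given-pair power runs from 20% to 82% with 25 per group and from 26% to 90% with 30.

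**Step 3: other definitions of power.** These depend on all four means. Three patterns were taken, each with a largest difference of d = 0.809. The Tukey entries come from 200,000 simulated trials per pattern; the ANOVA entries come from the noncentral F distribution.

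| Means | n | ANOVA significant | At least one Tukey pair | Given pair, only after significant ANOVA |
|---|---|---|---|---|
| 0, d/2, d/2, d | 25 | 65% | 65% | 57% |
| 0, 0, 0, d | 25 | 83% | 83% | 59% |
| 0, 0, d, d | 25 | 93% | 89% | 60% |
| 0, d/2, d/2, d | 30 | 74% | 74% | 68% |
| 0, 0, 0, d | 30 | 90% | 90% | 70% |
| 0, 0, d, d | 30 | 97% | 95% | 70% |

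The chance that no pair reaches significance is thus 11–35% with 25 per group and 5–26% with 30. That is a different quantity from the 30–40% miss rate for one given pair.

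**The case against.** The strongest reply is that the sentence in Sample Size Estimation is not false. It names its test, its significance level and its sample size, and the number is right for them. That stands: the arithmetic is sound, and the fault is that this test is not the one planned.

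A second reply is that given-pair power is a demanding definition and the plan does not say which definition it intends. The ANOVA comes first, and at 30 per group its power exceeds 80% in two of the three patterns. This is true and worth reporting. But the plan's statement describes a contrast between two groups, so the like-for-like figure is a given pair. Nor does the wider definition always rescue the 80%: with the other two means midway, both the ANOVA and the any-pair power are 65% (25 per group) or 74% (30 per group).

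A third is that 30 rather than 25 per group provides slack. It helps, but 30 is the ceiling and assumes no loss before the three-month call. Even then a given pair reaches only 70%.

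Finally, the plan never presents 0.809 as a clinically important difference; it is what 25 per group can detect with 80% power in a t-test. The practical change is in the detectable effect, from 0.81 to 0.98 or 0.89, all within the cited range of 0.5 to 1.0. That limits the consequence but leaves the mismatch in place.

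**Conclusion.** The concern holds. The WOMAC power statement does not belong to the planned WOMAC analysis. At 0.809, the planned Tukey test gives a given pair about 20 percentage points less power than stated with 25 analysed per group, and about 10 points less with 30. The result rests on the normality, common-SD and equal-size assumptions above, and the figure for 30 also on complete follow-up. The Tukey procedure itself is sound and keeps the familywise error at 5%. This should be fixed because it concerns a named primary endpoint and affects how non-significant pairs will be read.

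**What to change.** In Sample Size Estimation, replace the WOMAC power sentence with one for the planned test, for example:

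> With Tukey comparisons of all six pairs at 5% familywise, 25 (30) analysed per group gives about 60% (70%) power for a given pair at an effect size of 0.809, and 80% power at 0.98 (0.89).

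State whether 25 is the number expected to be analysed out of the 30 randomised per group. Optionally, add that the chance of at least one significant pair is 65–89% (74–95%), depending on the pattern of means, when the largest difference is 0.809.

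The cost is one or two sentences and a less favourable stated figure. It needs no extra patients and no change to the design or the analysis.
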